App Measure Selection: The preliminary usability and acceptance of the Salty app was measured to ensure alignment with the latest guidelines for feasibility trials while still addressing the core objective of evaluating the intervention for primary care patients with chronic pain. As part of this measurement selection, the mHealth App Usability Questionnaire (MAUQ) was used to measure preliminary usability, replacing the originally proposed Weiner and colleagues (2017, <https://implementationscience.biomedcentral.com/articles/10.1186/s13012-017-0635-3>) usability measure, due to its strong psychometric evidence and better alignment with construct definitions of evaluating a mobile app. Namely, the MAUQ provided a more robust evaluation of app usability, compared to the originally proposed measure. The MAUQ, the SaltyChP (i.e., a custom built measure developed by 2Morrow Inc. to help evaluate usability for product development and support marketability), and descriptives of app usage (i.e., total number of intervention arm patients that successfully engaged use of the app; days the app was used / proportion of days used that were possible; and, total number of badges earned out of the four that were possible) were used to evaluate preliminary usability and acceptance.

Aim 2. To assess feasibility of recruitment, study uptake, and completion of study assessments.

Feasibility Measure Selection: In alignment with standard measures used in feasibility randomized controlled trials, the following feasibility indicators were selected to assess recruitment procedures, retention, outcome measures' adequacy, and feasibility of implementing the intervention (i.e., Salty app):

1. Recruitment procedures: Ability to recruit a diverse sample of participants with various chronic pain diagnoses and exploring the reasons for ineligibility or study decline.
2. Retention: Will participants stay engaged in the study? Survey completion rates by arm and timepoint.
3. Outcomes measures adequacy: a) Are the measures acceptable, appropriate and relevant to the target population? b) Is there evidence of reliability and validity (including responsiveness to change) of measures in the target population?
4. Intervention implementation: a) Was the intervention delivered as intended? b) Were participants engaged with the program components?

Aim 3. To estimate the likely treatment efficacy effect size for a large RCT.

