1. **mHealth App Usability Questionnaire (MAUQ)**, administered at T2, is a 21-item survey that assesses mobile health (mHealth) app usability across three domains: ease of use and satisfaction (8 items), system information arrangement (6 items), and usefulness (7 items). It uses a 7-point Likert-type scale (1=strongly disagree to 7=strongly agree) and has established reliability and validity evidence (13).
2. **Salty Program for Chronic Pain Questionnaire (SaltyChP)** is a 6-item survey developed by 2Morrow, Inc., that explores specific aspects of the app (e.g., patients' satisfaction with various specific app features, patient ratings of helpfulness of the app for pain, likelihood to recommend the app to others) using Likert-type response scales. The survey includes two open-ended questions addressing what was helpful and what could be improved in the app. This survey was administered at both T2 and T3.

References

1. National Center for Complementary and Integrative Health. Pilot Studies: Common Uses and Misuses [Available from: <https://www.nccih.nih.gov/grants/pilot-studies-common-uses-and-misuses>].
8. Health NIO. PAIN INTERFERENCE A brief guide to the PROMIS Pain Interference instruments. 2018.

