The option to connect with a coach					
Earning passport stamps					
Opportunity to receive a Fitbit					
Seeing Fitbit data in the app					
Length of the program (100 days)					
Self-discovery surveys in the app to learn more about your mood, drinking, etc.					
Videos that you watched					
Other					

What other features were helpful to you?

Looking back to your use of the Salty program, what did you learn that may have changes the way you think about or manage your pain?

Health Care Resource Utilization (HCRU) Survey

During the past 3 months, did you receive any care, treatments, or tests for your chronic pain?

- ☐ No
☐ Unsure
☐ Yes
☐ Prefer not to say

This may include seeing or talking with a doctor or health professional, having laboratory tests, x-rays or other imaging, receiving treatment procedures, seeing an acupuncturist, massage or physical therapist, or some other care for your chronic pain.

In the past 3 months, do you think any of the following improved?

Satisfaction with my chronic pain care: _____
The communication with my providers about my pain and treatment: _____
Feeling more involved in my pain care: _____
Amount of pain care received (doctor visits, tests, procedures, etc): _____

Check all that apply

- ☐ More emergency room visits
☐ More urgent care visits
☐ More doctor visits (in person or virtually)
☐ More treatment procedures
☐ More tests
☐ More something else

Check all that apply

- ☐ Fewer emergency room visits
☐ Fewer urgent care visits
☐ Fewer doctor visits (in person or virtually)
☐ Fewer treatment procedures
☐ Fewer tests
☐ Fewer something else

mHealth App Usability Questionnaire

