The app adequately acknowledged and provided information to let me know the progress of my action.							
The navigation was consistent when moving between screens.							

The interface of the app allowed me to use all the functions (such as entering information, responding to reminders, viewing information) offered by the app.

☐ ☐ ☐ ☐ ☐ ☐ ☐ ☐

This app has all the functions and capabilities I expect it to have.

☐ ☐ ☐ ☐ ☐ ☐ ☐ ☐

Usefulness							
	Strongly Disagree	Disagree	Somewhat Disagree	Neither Agree or Disagree	Somewhat Agree	Agree	Strongly Agree
The app would be useful for my health and well-being.							
The app improved my access to health care services.							
The app helped me manage my health effectively.							
The app made it convenient for me to communicate with my health care provider.							
Using the app, I had many more opportunities to interact with my health care provider.							
I felt confident that any information I sent to my provider using the app would be received.							
I felt comfortable communicating with my health care provider using the app.							

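### Four of the seven MAUQ usefulness items ask about provider contact that is not among the app's listed features, so the usefulness score may be lowered or lost

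*Combined protocol and SAP*

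**What the plan says.** The section on outcome measures for the intervention group describes the MAUQ as a 21-item questionnaire given at T2, with three domains: "ease of use and satisfaction (8 items), system information arrangement (6 items), and usefulness (7 items"). On the response format it says: "It uses a 7-point Likert-type scale (1=strongly disagree to 7=strongly agree"). Under Aim 1, App Measure Selection, the MAUQ replaces the usability measure first proposed, partly for its "better alignment with construct definitions of evaluating a mobile app". It is used together with the SaltyChP questionnaire and descriptive app-usage data.

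Appendix 1 prints the instrument. The last four usefulness items all concern contact with a provider. The first of them reads "The app made it convenient for me to communicate with my health care provider". The second asks whether the app gave the user more chances for such contact. The third reads "I felt confident that any information I sent to my provider using the app would be received". The fourth asks how at ease the user felt with this kind of contact.

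The Background describes an app that delivers ACT and CBT content, and the eligibility criteria call it a self-management program. The SaltyChP feature ratings in Appendix 1 cover lessons, topics, check-ins, insights, stamps, Fitbit, in-app surveys and videos. The nearest entry to provider contact is "The option to connect with a coach".

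The Data collection section lets participants skip questions. It then excludes a participant from a measure if any subscale item needed for its total is missing. The documents do not say whether the MAUQ is scored by domain or as a total, and give no rule for items that do not apply.

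**The concern.** An item about a function that the user did not find in the app cannot tell us whether the app is useful. With seven agreement categories and no way to mark the item as not applicable, the user can disagree, choose the neutral category, guess, or skip. Disagreement lowers the score. A neutral answer also lowers it whenever the other ratings are above neutral. Skipping, perhaps the most natural response, costs the whole score under the complete-item rule.

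At stake is how the usability results for Aim 1 are read. A low usefulness mean could be taken as a verdict on the program when it partly reflects the fit between questionnaire and app. A mean from complete responders only would describe a selected group. The same information bears on Aim 2, which asks whether the outcome measures are relevant to the target population. Responses to these four items would help answer that, but no item-level reporting is planned.

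**Working it through.** **Inputs from the documents.** The domain sizes are 8, 6 and 7 (Outcome measures, Intervention Group), and the response scale runs from 1 to 7. Counting the items printed in Appendix 1 gives the same sizes, and 8 + 6 + 7 = 21 reproduces the stated length. Four usefulness items name a provider. They are 4/7 = 57% of the domain and 4/21 = 19% of the questionnaire.

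**Assumed inputs.** The documents give no MAUQ responses or skip rates. Let *a* be the rating on all other items, *b* the rating on the four provider items, and *s* the skip rate per provider item.

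**Effect on the mean.**

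- Usefulness = (3a + 4b)/7, a fall of 4(a − b)/7 from *a*.
- 21-item mean = (17a + 4b)/21, a fall of 4(a − b)/21 from *a*.

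| a | b | Usefulness (fall) | 21-item mean (fall) |
|---|---|---|---|
| 6 | 1 | (18 + 4)/7 = 3.14 (2.86) | (102 + 4)/21 = 5.05 (0.95) |
| 6 | 4 | (18 + 16)/7 = 4.86 (1.14) | (102 + 16)/21 = 5.62 (0.38) |
| 5 | 1 | (15 + 4)/7 = 2.71 (2.29) | (85 + 4)/21 = 4.24 (0.76) |
| 7 | 1 | (21 + 4)/7 = 3.57 (3.43) | (119 + 4)/21 = 5.86 (1.14) |
| 5 | 4 | (15 + 16)/7 = 4.43 (0.57) | (85 + 16)/21 = 4.81 (0.19) |
| 4 | 4 | 4.00 (0) | 4.00 (0) |

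In the first row, a user who agrees with everything else falls below the scale midpoint of 4 on usefulness. In the last row there is no effect. Leaving out the four items returns both means to *a* in every row.

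**Effect of skipping under the complete-item rule.** If the four items are skipped independently, the share of scores lost is 1 − (1 − s)^4. If they are skipped together, it is *s*.

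| s | Lost, independent skipping | Lost, skipped together |
|---|---|---|
| 5% | 18.5% | 5% |
| 10% | 34.4% | 10% |
| 20% | 59.0% | 20% |

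Items that fail to apply for the same reason are likely to be skipped together, so the right-hand column is probably closer to practice.

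**The case against.** Several points on the other side carry weight.

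- **The missing function is inferred.** A reader might infer that the app has no provider contact at all. The documents do not say so. The SaltyChP list is a set of helpfulness ratings with a row for other features, and the copy at hand has no text under the intervention heading, where a description may once have stood. Some users may also count the coach as a provider. This stands as a limit on wording. It does not remove the problem: if some users count the coach and others do not, the four items mean different things to different people.
- **The MAUQ is not the whole of Aim 1.** A reader might infer that the main Aim 1 score is compromised. No measure is named as main. SaltyChP and the usage data are untouched, and SaltyChP asks directly about help with pain, worth of time and willingness to recommend.
- **No decision hangs on the score.** There is no MAUQ threshold or progression rule, and scoring by domain, which may already be intended, leaves 14 of the 21 items unaffected.
- **The instrument was chosen for its psychometric evidence.** Promoting an unvalidated three-item score to lead result after data collection would give that up. The cut is also a matter of judgement, since other retained items about access to or receipt of health care services could be challenged in the same way. This stands, and is why the published score should keep the lead.

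The reply that Aim 2 already examines whether measures are relevant is only partial, because no method for doing so is given.

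**Conclusion.** The point holds as a modest one. The count of four in seven, the lack of a not-applicable option in the usefulness grid, and the complete-item exclusion rule can all be seen in the documents, and nothing in them deals with the combination. The usefulness domain and any MAUQ total may be lowered or lost for reasons unrelated to usability.

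The size depends on assumed responses. For other-item ratings of 5 to 7 and provider-item ratings of 1 to 4, usefulness falls by 0.57 to 3.43 points and the 21-item mean by 0.19 to 1.14. If all ratings are neutral there is no fall. The loss from skipping depends on unknown skip rates and on how they cluster.

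A reader might infer that scores were in fact depressed, or that only a few participants gave usable scores. The documents contain no MAUQ results and support neither statement.

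**What to change.** 1. Report the three MAUQ domains separately, so that ease of use and system information stand on their own.
2. Keep the seven-item usefulness score as the lead result, and show beside it a sensitivity score from the three items that do not mention a provider.
3. Score each domain as the mean of answered items, written as an explicit exception to the complete-data rule in the Data collection section, so that skipping an inapplicable item does not remove the person.
4. Report the skip rate and response distribution of each of the four items. This also shows how many lead scores rest on fewer than seven items: for a person who skips all four, the lead and sensitivity scores coincide.

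The cost is rescoring and a few extra table rows, with no new data collection. The reduced score does not carry the published validity evidence and should be labelled accordingly.
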